## 1.3.3. End of Treatment and Follow-Up

**End of Treatment Visit:** Obtain these assessments if not completed in the last week (last 6 weeks for tumor assessments up to 24 months).

**Follow up:** At least 28 days, and no more than 35 days after discontinuation of treatment participants will return to undergo review for resolution of any treatment related toxicity. Participants continuing to experience toxicity at this point following discontinuation of treatment will continue to be followed at least every 4 weeks until resolution or determination, in the clinical judgment of the Investigator, that no further improvement is expected. Participants discontinuing treatment for reasons other than progression of disease will continue to perform tumor assessments until PD up to approximately 24 months (cycle 35).

Visit Identifier	End of Treatment	Follow-up	Notes  (X) refer to specific footnote when the measurement may be optional /repeat measurement might not be required.	
Visit Window	±2 days	±7 days		
Physical examination	X			
Weight	X			
Contraception check (as appropriate)	X	X	The participant may be contacted by phone to confirm contraception is still appropriate per the protocol. Males and females of childbearing potential must be contacted after study intervention discontinuation to ensure that they continue to use appropriate contraception for at least 98 and 35 days, respectively, after the last dose of study intervention.	
Laboratory				
Pregnancy test	X	X	The pregnancy test should be performed at the clinical site's local laboratory. Where that is not possible, participants will provide the laboratory test results carried out at a non-clinical site laboratory, eg, by telephone, and bring a copy of the laboratory test results at the next cycle visit. The copy of the laboratory test results must be retained in the participant's file at the clinical site for documentation purposes.	
Tumor Assessments				

Visit Identifier	End of Treatment	Follow-up	Notes  (X) refer to specific footnote when the measurement may be optional /repeat measurement might not be required.
Visit Window	±2 days	±7 days	
CT and MRI Scan or Equivalent	(X)		Tumor assessment should be repeated at the end of treatment if more than 6 weeks have passed since the last evaluation. Tumor assessment should not be repeated at the end of treatment if progression occurs when the participant has shifted to the local clinical practice.
Other Clinical Assessments			
Adverse Events	X	X	

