## 6.5. Concomitant Therapy

All concomitant medications and non-drug supportive interventions should be recorded in the CRF until the participant has completed 35 cycles of treatment (approximately 24 months). After cycle 35 the data will be reported in the medical chart, but not collected in the CRF.

Any medication or vaccine (including over-the-counter or prescription medicines, vitamins, and/or herbal supplements) that the participant is receiving at the time of enrollment or receives during the study must be recorded along with:

- Reason for use
- Dates of administration including start and end dates

The Medical Monitor should be contacted if there are any questions regarding concomitant or prior therapy.

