# 7. DISCONTINUATION OF STUDY INTERVENTION AND PARTICIPANT DISCONTINUATION/WITHDRAWAL

## 7.1. Discontinuation of Study Intervention

In rare instances, it may be necessary for a patient to permanently discontinue study intervention. If study intervention is permanently discontinued, the participant will remain in the study to complete all remaining scheduled assessments.

See Table 3 for dose modification recommendations due to adverse events.

Discontinuation of study intervention for abnormal liver function should be considered by the investigator when a participant meets one of the conditions outlined Appendix 6 or if the investigator believes that it is in best interest of the participant.

If a clinically significant finding is identified (including, but not limited to changes from baseline in QT interval corrected using Fridericia's formula (QTcF) after enrollment (Appendix 7), the investigator or qualified designee will determine if the participant can continue in the study and if any change in participant management is needed. This review of the ECG printed at the time of collection must be documented. Any new clinically relevant finding should be reported as an AE.

If a clinically significant finding is identified after enrollment, the investigator or qualified designee will determine if the participant can continue in the study and if any change in participant management is needed.

See the schedule of activities (SoA) for data to be collected at the time of intervention discontinuation and follow-up and for any further evaluations that need to be completed.

Note that discontinuation of study intervention does not represent withdrawal from the study.

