5.2.4. Date of last contact

The date of last contact will be derived for patients not known to have died at the data cutoff date using the latest complete date (i.e. imputed dates will not be used in the derivation) among the following:

- All patient assessment dates e.g. tumor assessments
- Start and stop dates of concomitant therapies including non-drug treatments or procedures
- Start and end dates of anti-cancer therapies administered after study treatment discontinuation including systemic therapy, radiation, and surgeries,
- AE start and end dates
- Date of first and last dose
- Vital sign weight assessment dates
- Date of discontinuation on disposition CRF pages (do not use if reason for discontinuation is lost to follow-up or death).

Only dates associated with actual examinations of the patient will be used in the derivation. Dates associated with a technical operation unrelated to patient status such as the dates data were entered into the CRF will not be used.

Assessment dates after the data cutoff date will not be applied to derive the last contact date.

DMB02-GSOP-RF02 4.0 Statistical Analysis Plan Template 01-Nov-2018 PFIZER CONFIDENTIAL Page 17 TMF Doc ID: 98.03

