Anti-cancer therapies will be collected in short term follow up only (up to 35 days after treatment discontinuation)

Incomplete dates for new anti-cancer therapy will be imputed as follows and will be used to determine censoring dates for efficacy analyses:

- The end date of new anti-cancer therapy will be included in the imputation for start date of new anti-cancer therapy. If the end data of new anti-cancer therapy is:
 - completely missing then it will be ignored in the imputations below,
 - partially missing with only year available then the imputations below will consider 31DECYYYY as the end date of the new anti-cancer therapy, or
 - partially missing with only month and year available then the imputations below will consider the last day of the month for MMMYYYY as the end date of the new anti-cancer therapy.
- For participants who have not discontinued study treatment at the time of the data cutoff date, last dose of study treatment is set to the data cutoff date in the imputations below.
- If the start date of new anti-cancer therapy is completely or partially missing then the imputed start date of new anti-cancer therapy is:

= 31DECYYYY, if only Year is available and Year < Year of min [max (PD date + 1, last dose of study treatment + 1), end date of new anti-cancer therapy]

= Last day of the month, if both Year and Month are available and

Year = Year of min [max (PD date + 1, last dose of study treatment + 1), end date of new anti-cancer therapy]

Month < Month of min [max (PD date + 1 day, last dose of study treatment + 1 day), end date of new anti-cancer therapy]

= min [max (PD date + 1, last dose of study treatment + 1), end date of new anticancer therapy], for all other cases.

AE Onset Date

The following imputation rules apply if the event is unique for a participant or it is the first of a series of similar events; otherwise, the AE Onset Date will not be imputed:

- If the AE Collection Date is not missing, is less than the Date of First Exposure to Treatment, and is less than the AE Stop Date, then AE Onset Date is set to the Date of AE Collection.
- If the Previous Visit Date is greater than the Date of First Exposure to Treatment and less than the AE Stop Date, the AE Start Date is set to the previous visit date. DMB02-GSOP-RF02 4.0 Statistical Analysis Plan Template 01-Nov-2018 PFIZER CONFIDENTIAL Page 22 TMF Doc ID: 98.03

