6.5.4. Concomitant Medications and Nondrug Treatments

Concomitant medications and non-drug treatments received by participants during the study will be summarized for the Safety Analysis Set.

Concomitant medications refer to all medications which started prior to first dose of study treatment and continued during the on-treatment period (see section 5.2) as well as those started during the on-treatment period. Concomitant medications will be coded in the WHO Drug coding dictionary and will be tabulated by Anatomical Therapeutic Chemical (ATC) Classification level 2 and preferred term in descending order of frequency. In case of equal frequency regarding drug class (respectively drug name), alphabetical order will be used. A participant will be counted only once within a given drug class and within a given drug name, even if he/she received the same medication at different times. Preferred Terms will be reported under each ATC class that it is included under within WHO Drug (no primary path is available in WHO Drug)

Concomitant non-drug treatments refer to all non-drug treatments administered during the on-treatment period. Non-drug treatments will be coded with the most current version of MedDRA and will be summarized by MedDRA's SOC and PT in descending order of frequency.

Participants will be counted only once per PT even if he/she received the same treatment multiple times.

Any medications or non-drug treatments, aside from anti-cancer treatments described in section 6.5.1, which were only administered prior to treatment start will be listed but not summarized.

DMB02-GSOP-RF02 4.0 Statistical Analysis Plan Template 01-Nov-2018 PFIZER CONFIDENTIAL Page 36 TMF Doc ID: 98.03

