6.5.5. Subsequent Anti-Cancer Therapies/Procedures

Subsequent Anti-Cancer Therapies and Procedures are defined as therapies entered on the short term follow up in the 'Follow-up Cancer Therapy', 'Follow-up Radiation Therapy', and 'Follow-up Surgery' CRF pages. The number and percentage of participants within each category (medication therapy, radiation therapy, and surgeries) will be provided.

Medications will be coded using the WHO Drug coding dictionary and will be tabulated by preferred term in descending order of frequency.

Analyses will be based on the ITT analysis set.

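### Subsequent anti-cancer therapy is to be collected only to 35 days after lorlatinib stops, but scans that depend on its start date continue to progression (minor, cheap to repair)

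*SAP*

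**What the plan says.** **Collection of therapy stops early.** SAP 5.3.1: "Anti-cancer therapies will be collected in short term follow up only (up to 35 days after treatment discontinuation". SAP 6.5.5 says subsequent therapies and procedures "are defined as therapies entered on the short term follow up" CRF pages. SAP 2.2 sets short-term follow-up at up to 35 days and rules out long-term follow-up.

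**Scans do not stop.** Protocol 1.3.3: "Participants discontinuing treatment for reasons other than progression of disease will continue to perform tumor assessments until PD up to approximately 24 months". Protocol 7.1: "If study intervention is permanently discontinued, the participant will remain in the study to complete all remaining scheduled assessments". SAP 6.2.7 and 6.2.8 describe six-weekly scans to PD whether or not a new therapy has begun. Protocol 4.4 ends the trial 12 months after the last patient's first visit.

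**The start date is used.** OR drops response data after a new therapy (SAP 6.1.1), and IC-OR follows OR (6.2.2). PFS and TTP are censored at the last adequate assessment before it (6.2.7, 6.2.8). DoR and IC-DoR take the PFS rules (6.2.5, 6.2.6).

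**Some text is wider.** Protocol 6.5 says a medicine or vaccine that a participant "receives during the study must be recorded along with" its reason and dates. Protocol 7.1 adds that "discontinuation of study intervention does not represent withdrawal from the study". The date of last contact in SAP 5.2.4 uses "Start and end dates of anti-cancer therapies administered after study treatment discontinuation including systemic therapy, radiation, and surgeries", with no 35-day limit.

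**The concern.** A participant who stops lorlatinib without PD, for toxicity or refusal for example, is still scanned. If a new therapy begins after day 35, six endpoints need its start date, and SAP 5.3.1 read literally does not provide for it. The imputation rules in the same section complete partial dates of recorded therapies. They cannot find an unrecorded one.

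Two outcomes are possible, and they are alternatives:

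- If scans continue and the 35-day rule is followed, scans made on another drug are credited to lorlatinib. For OR and IC-OR this can only add responders. For DoR, IC-DoR, PFS and TTP the direction depends on how well the later therapy works.
- If SAP 2.2 is read as ending all collection, that gap mostly disappears, but scans required by protocol 1.3.3 and 7.1 are lost for these participants.

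Two programmers could follow different passages and censor differently.

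**Working it through.** **1. The plan's own figure.** Exact (Clopper-Pearson) lower limits are 30.6% for 26/60 (43.3%) and 29.1% for 25/60, so the plan's statement for 60 participants at about 43% holds. Allowing for 15% dropout, 60/0.85 = 70.6, against 70 planned. With 70 in the denominator, 29/70 gives 29.77% (fails) and 30/70 gives 31.09% (succeeds). Success therefore means 30 or more responders. P(X ≥ 30) is 1.52% at a true ORR of 30% and 55.5% at 43%.

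**2. Scans outside the therapy window.** Suppose the last-enrolled participant stops without PD on day 91.

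- Capture ends on day 91 + 35 = 126.
- Six-weekly scans then fall on days 168, 210, 252, 294 and 336: 5 scans by day 365.
- If the first visit is screening 28 days before dosing, the limit is day 337 and the last scan is borderline (4 to 5).
- An early enrollee followed to about day 730 could have 14 (days 168 to 714). The enrolment period is not given.

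**3. False responders.** Assumed: share stopping without PD d = 5% to 15%; share of those switching unrecorded s = 0.5 or 1. Response to the later therapy r runs from 6.9% (chemotherapy figure, protocol section 2) to 30% (protocol 9.2). At a true ORR of 30%, 70% are non-responders.

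Expected number = 70 × d × 0.70 × s × r

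- Lowest: 70 × 0.05 × 0.70 × 0.5 × 0.069 = 0.08
- Highest: 70 × 0.15 × 0.70 × 1 × 0.30 = 2.2

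P(success) = P(Bin(70, 0.30 + 0.70·d·s·r) ≥ 30), against 1.5% with full capture:

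| d | r | s = 0.5 | s = 1 |
|---|---|---|---|
| 5% | 6.9% | 1.6% | 1.7% |
| 5% | 30% | 1.9% | 2.5% |
| 15% | 6.9% | 1.8% | 2.1% |
| 15% | 30% | 3.1% | 5.7% |

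One extra responder changes the outcome only if the true count is exactly 29. That has probability 1.2% at an ORR of 30% and 9.3% at 43%.

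**4. Duration of response.** Assumed exponential with the median of 5.6 months in protocol 2.2, so λ = ln 2/5.6. Stopping hazard μ = λd/(1−d). Switch at L = 36 days after stopping (36/30.4375 months). Later hazard hλ with h = 0.5 or 2. Without the missing censoring, for t > L:

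S(t) = (1−s)e^(−λt) + s[e^(−μ(t−L))e^(−λt) + ∫₀^(t−L) μe^(−μu) e^(−λ(u+L)) e^(−hλ(t−u−L)) du]

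With correct censoring the median is 5.6 months and S(12) = 22.6%.

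| d | s | Median, h = 0.5 / 2 | S(12), h = 0.5 / 2 |
|---|---|---|---|
| 15% | 1 | 5.72 / 5.44 | 24.8% / 20.4% |
| 15% | 0.5 | 5.66 / 5.52 | 23.7% / 21.5% |
| 5% | 1 | 5.64 / 5.55 | 23.3% / 21.9% |

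The SAP does not plan a 12-month rate for DoR; it is used here only as a yardstick. With 30 responders and no censoring its standard error is √(0.2264 × 0.7736/30) = 7.6 points. The largest shift, 2.2 points, is 0.29 of that.

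**The case against.** The best reply is that the documents already provide for later capture. Protocol 6.5 is broad, protocol 7.1 keeps these participants in the study, and SAP 5.2.4 has no day limit. SAP 6.5.5 defines a descriptive table. So does SAP 6.5.4, which tabulates earlier medicines continued on treatment "as well as those started during the on-treatment period". Neither proves that later drugs go uncollected. SAP 2.2 may mean only that there is no survival follow-up, since overall survival is not an endpoint.

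Much of this stands. A reader might infer that later therapies will certainly go unrecorded; the documents do not support that, because they conflict and the CRF is not visible. But the wider text does not settle the matter. The quoted protocol 6.5 sentence covers medicines and vaccines, not radiation or surgery. SAP 5.2.4 sets no collection window and serves another purpose. No SAP passage names concomitant-medication data as a source for the new-therapy date. The protocol 1.3.3 schedule has no row for subsequent therapy and no concomitant-medication entry at Follow-up. SAP 5.3.1 says 'only', in the section that supplies the censoring dates.

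It is also fair that every rate producing an effect is assumed, and that the effect is small. That limits the importance of the point but does not remove the conflict.

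**Conclusion.** The point holds as a minor inconsistency. SAP 2.2, 5.3.1 and 6.5.5 need reconciling with protocol 1.3.3 and 7.1 and with SAP 6.2.7 and 6.2.8.

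Under the assumed ranges the gap gives 0.08 to 2.2 false responders of 70 and moves the median DoR from 5.6 to between 5.44 and 5.72 months, well inside sampling error. Only OR and DoR were computed; nothing is claimed about the size for IC-OR, IC-DoR, PFS or TTP. The documents give no rate of stopping without PD or of later therapy. The 15% in SAP 5.1.1 is an allowance for non-evaluable participants and should not be read as such a rate.

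A reader might infer that the primary conclusion is in danger. The documents do not support that. The 5.7% chance of success at a true ORR of 30% needs 15% stopping without PD, all of them switching unrecorded, and 30% responding. Apart from such a corner, the error matters only when the count lies near 29 versus 30 of 70. Nor should the two harms be added together: only one can arise, depending on how SAP 2.2 is read.

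**What to change.** 1. **SAP 5.3.1.** Replace the 'only' sentence with: *Start date and type (and site, if not already on the CRF, for radiation or surgery) of each subsequent anti-cancer therapy will be collected at short-term follow-up and at each later post-treatment tumour assessment or contact, until PD by both ICR and investigator, death, withdrawal or End of Trial, whichever is first.* Requiring PD by both assessors keeps the date available for ICR endpoints after investigator-only PD. Site supports the SAP 6.2.2 rule that extracranial surgery or radiotherapy does not affect IC-OR.
2. **SAP 6.5.5.** Widen the definition to match, keeping the three named CRF pages.
3. **SAP 2.2.** Replace the sentence on long-term follow-up with: *There is no separate survival follow-up. For participants who stop lorlatinib without PD, tumour assessments (as in protocol 1.3.3, until PD, up to approximately 24 months and not beyond End of Trial), subsequent anti-cancer therapy (as in Section 5.3.1) and deaths continue to be collected. Safety follow-up required by the protocol is unchanged.*
4. **Protocol 1.3.3, at the next amendment.** Add a column for post-treatment tumour assessments, which the table lacks, and a row for subsequent anti-cancer therapy marked there and at Follow-up.

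**Cost.** Slightly more CRF entry for an assumed 4 to 10 of 70 participants, most of whom already return for scans, plus occasional contacts after investigator-only PD. The schedule change needs the amendment's IRB/IEC review (protocol 10.1.1). No new procedure is added.

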2.1.1. Primary Estimand

The primary estimand is the treatment effect of Lorlatinib from the time of first dose until progression is met, death or subsequent anti-cancer therapy is administered regardless of tolerability or duration on treatment. It includes the following 4 attributes:

- Population: Participants with Anaplastic Lymphoma Kinase (ALK)-Positive Non-Small Cell Lung Cancer (NSCLC) Whose Disease Progressed After One Prior Second-Generation ALK Tyrosine Kinase Inhibitor (TKI), as defined by the inclusion and exclusion criteria, and who receive at least one dose of lorlatinib
- Variable: Confirmed Objective Response according to RECIST 1.1 per ICR, defined as CR or PR from the date of first dose until PD, death, or start of new anticancer therapy
- Intercurrent event: All data after the intercurrent event "start of subsequent anticancer therapy treatment" will be excluded; non adherence to treatment is not an intercurrent event; assessments are considered regardless of gaps in assessments
- Population-level summary: ORR, ie percentage of participants with confirmed complete response [CR] or confirmed partial response [PR] and associated exact CI

DMB02-GSOP-RF02 4.0 Statistical Analysis Plan Template 01-Nov-2018 PFIZER CONFIDENTIAL Page 8 TMF Doc ID: 98.03

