6. ANALYSES AND SUMMARIES

6.1. Primary Endpoint

6.1.1. Confirmed OR by ICR

Analysis set: ITT: All enrolled participants who take at least 1 dose of Lorlatinib

Analysis methodology:

• Objective Response Rate (ORR) defined as the percentage of patients with a confirmed best overall response (BOR) of CR or PR according to RECIST v1.1

BOR will be determined based on reported overall responses at different evaluation timepoints by the independent radiologist from the date of treatment start until documented disease progression or start of new anti-cancer therapy, according to the following rules:

- CR = at least two determinations of CR at least 4 weeks apart and documented before progression and start of new anti-cancer therapy
- PR = at least two determinations of PR or better (and not qualifying for a CR) at least 4 weeks apart and before progression and start of new anti-cancer
- SD (for patients with at least one measurable lesion at baseline) = at least one SD assessment (or better and not qualifying for CR or PR) ≥ 6 weeks after date of treatment start and before progression and the start of new anti-cancer therapy
- Non-CR/Non-PD (for patients with only non-target disease at baseline) = at least one Non-CR/Non-PD assessment (or better and not qualifying for CR or PR) ≥ 6 weeks after date of treatment start and before progression and the start of new anti-cancer therapy
- PD = progression ≤ 14 weeks after date of treatment start and not qualifying for CR, PR or SD
- Not Evaluable (NE) = all other cases.

Clinical deterioration will not be considered as documented disease progression.

- patients without documented CR or PR will be considered as non-responders
- Exact CI for a binomial proportion for ORR using the Clopper-Pearson method
- best % changes vs baseline as defined below under Summaries used for Reporting DMB02-GSOP-RF02 4.0 Statistical Analysis Plan Template 01-Nov-2018 PFIZER CONFIDENTIAL Page 24 TMF Doc ID: 98.03

• % change vs baseline across visits as defined below under Summaries used for Reporting

Intercurrent events and missing data:

- data on response after subsequent anti-cancer therapy is administered will be excluded
- participants with death prior to first post-baseline assessment, inadequate baseline assessment, new anti-cancer therapy started prior to first post-baseline assessment, and all post-baseline disease assessments missing will also be considered as non-responders.

Summaries used for reporting:

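### When lorlatinib stops before progression, a missing start date for new anti-cancer therapy can be imputed to the day after progression, later than the 35-day window in which that therapy is recorded

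*SAP*

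**What the plan says.** SAP 5.3.1 (Missing Dates) imputes an incomplete start date of new anti-cancer therapy in three branches. Call max(PD + 1, last dose + 1), capped by the end date of the new therapy, the reference date.

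- Only the year is known and it is earlier than the reference year: 31 December of the recorded year. The SAP's wording begins "31DECYYYY, if only Year is available and Year < Year of min [max (PD date + 1".
- Month and year are known, the year equals the reference year and the month is earlier: last day of that month.
- Everything else: "min [max (PD date + 1, last dose of study treatment + 1), end date of new anticancer therapy], for all other cases". If the end date of the new therapy is "completely missing then it will be ignored in the imputations below", only the larger of PD + 1 and last dose + 1 remains.

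The imputed dates "will be used to determine censoring dates for efficacy analyses". For the primary endpoint, SAP 6.1.1 states that "data on response after subsequent anti-cancer therapy is administered will be excluded". SAP 6.2.5, 6.2.7 and 6.2.8 censor DoR, PFS and TTP at the last adequate scan before new therapy.

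The same subsection of SAP 5.3.1 limits what is recorded: "Anti-cancer therapies will be collected in short term follow up only (up to 35 days after treatment discontinuation". Protocol 1.3.3 continues scans beyond that: "Participants discontinuing treatment for reasons other than progression of disease will continue to perform tumor assessments until PD". SAP 6.2.7 likewise continues six-weekly scans after a new therapy has begun. SAP 2.2, however, describes follow-up to 35 days after discontinuation and no long-term follow-up.

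**The concern.** The default branch takes the later of two anchors, and one of them is the outcome. When a participant stops lorlatinib without PD, begins another drug and progresses later, PD + 1 is the later anchor. A start date set to PD + 1 cannot precede PD, so neither the exclusion nor the censoring can act on that record.

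The date can also contradict the collection rule. A therapy recorded at short-term follow-up had begun by about last dose + 35 days, whereas PD may come months later.

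Two results are at stake. A partial response seen and confirmed on the new drug could count in the primary ORR. A PD on the new drug would be an event for PFS, TTP or DoR, where the plan intends an earlier censoring. Elsewhere in SAP 5.3.1 missing start dates are handled more cautiously: a worst case for adverse events and concomitant medications, and the first day of the month or year for other partial start dates.

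**Working it through.** **The plan's own threshold.** The Clopper-Pearson 95% lower limit for x responders of n is the 2.5% quantile of Beta(x, n − x + 1). SAP 5.1.1 states that 60 participants at an ORR of about 43% give a lower limit above 30%. For 26/60 = 43.3% the limit is 30.6%, so the statement is reproduced. At the planned N = 70, 29/70 gives 29.77% (fails the rule in SAP 5.1.2) and 30/70 gives 31.09% (passes).

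**The date rule applied literally.** Last dose is 01 Jun 2021 throughout, so the collection window ends 35 days later, on 06 Jul 2021. The dates are illustrative. A participant without PD is assumed to contribute no PD date to the maximum, which the SAP does not state.

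| Recorded start | PD | Recorded end | Imputed start | Position |
|---|---|---|---|---|
| missing | 20 Sep 2021 | none | 21 Sep 2021 | after PD |
| 2021 | 20 Sep 2021 | none | 21 Sep 2021 | after PD |
| 2021 | 20 Jan 2022 | none | 31 Dec 2021 | before PD |
| missing | 20 Sep 2021 | 15 Aug 2021 | 15 Aug 2021 | before PD |
| missing | none | none | 02 Jun 2021 | last dose + 1 |
| missing | 28 May 2021 | none | 02 Jun 2021 | after PD, nothing miscredited |
| Jun 2021 | 20 Sep 2021 | none | 30 Jun 2021 | before PD |
| Jun 2021 | 20 Jan 2022 | none | 21 Jan 2022 | after PD, contradicts the recorded month |

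Rows 1 and 2 are the fault. Row 8 is a related gap: a known month in a year before the reference year meets neither special branch and falls to the default. Rows 3 and 4 precede PD but still lie after 06 Jul 2021.

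**One record followed through** (illustrative). Last dose day 60 for toxicity, no PD. New therapy is recorded at a day-90 follow-up visit with start and end unknown. PR on days 100 and 142, PD on day 210.

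- Imputed start: max(210 + 1, 60 + 1) = day 211.
- Latest start the collection rule allows: 60 + 35 = day 95.
- As written: the PRs are 142 − 100 = 42 days apart (at least 28 are needed) and precede both PD and day 211, so the participant is a responder. PD comes 210 − 142 = 68 days after the last adequate scan, within the 98-day limit, so PFS has an event at day 210.
- With the start capped at the follow-up page date: min(211, 90) = day 90. Both PRs are excluded, the participant is a non-responder, and PFS is censored at the last adequate scan before day 90. A cap at day 95 gives the same classification.

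**The case against.** Four points stand against giving this much weight.

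1. The chain of conditions is long. For the ORR error, one participant must stop lorlatinib without PD and without a confirmed response, start a new drug within about 35 days, have no usable start date and no end date before PD, have a PR confirmed by central review on the new drug, and then progress. The documents give no rate of missing dates, and Protocol 10.1.7 requires ongoing source data verification.

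2. The late scans are not certain to exist. Under SAP 2.2, read literally, the PRs and PD in the worked record would not be collected. Protocol 1.3.3 and SAP 6.2.7 do plan them. The error is reachable under the latter two, so the sections need reconciling.

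3. A single miscredited response matters only if the correct count is exactly 29. At a true ORR of 30% that probability is 2.76% − 1.52% = 1.24%; at 43% it is about 9%. The chance of passing at a true ORR of 30% rises from 1.5% to 2.8% only if one response is miscredited in every trial, which nothing in the documents supports.

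4. PD + 1 has a purpose. If dosing stops on suspected progression and a scan documents PD a few days later, a start after PD is the likely sequence.

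A reader might infer that every missing or year-only start is placed after PD, and so that the new-therapy rule is disabled whenever a date is imputed. The table shows otherwise. A year-only date before the reference year goes to 31 December, a recorded end date caps the start, and a known earlier month in the reference year is respected. With no PD the start is last dose + 1, which excludes all later response data.

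**Conclusion.** Wrong as written, in a narrow case. When lorlatinib stops before PD, the start date is missing or known only as the reference year, and no end date before PD is recorded, SAP 5.3.1 yields PD + 1. That date can lie well outside the SAP's own collection window, and it prevents the exclusion and censoring for that record.

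For ORR the error can only be upward. For PFS, TTP and DoR a later event replaces an earlier censoring. It may be tempting to conclude that the medians are inflated, but the direction of that bias is not fixed.

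The assumed frequency is 0 to 1 of 70. The conclusion also rests on scans continuing after day 35 as Protocol 1.3.3 and SAP 6.2.7 plan. The expected effect on the trial is small. The case for correcting it is that the rule can produce an impossible date and that one responder separates failure from success at 29 against 30 of 70.

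**What to change.** Replace the derivation with: imputed start = min[max(PD date + 1, last dose + 1), end date of the new therapy, date of the follow-up page on which the therapy was recorded (at latest last dose + 35 days)], always held within any recorded month or year. This keeps the existing anchors and also resolves row 8 of the table, where the result becomes 30 Jun 2021. State what happens when there is no PD, and which PD date is meant (central, investigator or intracranial). Reconcile SAP 2.2 with Protocol 1.3.3 and SAP 6.2.7 on scans after day 35.

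A sensitivity analysis with last dose + 1 is optional. It should not be the primary rule, because it would censor true PD events documented shortly after the last dose. For example, with last dose 01 Jun, PD on 06 Jun and a follow-up page on 01 Jul, last dose + 1 is 02 Jun and the PD is lost. The capped rule gives min[max(07 Jun, 02 Jun), 01 Jul] = 07 Jun and keeps it.

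The cost is one more term in the derivation, and occasionally a slightly lower responder count or an earlier censoring date. What remains is bounded: the imputed start can be late by at most 35 − 1 = 34 days, assuming systemic therapy begins no earlier than last dose + 1, since Protocol 6.5.1 does not allow it during study treatment. The change should be made before database lock.
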